7.8. Safety Surveillance

Gilead PVE periodically reviews accumulating safety data across completed and ongoing studies within the GS-4875 development program to detect serious and unexpected suspected adverse reactions and clinically important increased rates of previously recognized serious adverse reactions. If, during the periodic review of safety data from clinical studies, a significant numerical imbalance is observed for an AE across treatment groups based on predefined reporting thresholds, a Safety Assessment Committee (SAC) will review unblinded safety data and determine if any actions are necessary to protect subjects involved in the GS-4875 development program. In order to preserve the scientific integrity of the trial data, the SAC members will be Gilead employees who are not involved in the conduct and analysis of studies within the GS-4875 development program.

8. STATISTICAL CONSIDERATIONS

8.1. Analysis Objectives and Endpoints

8.1.1. Analysis Objectives

The objectives of the study are described in Section 2.

8.1.2. Study Endpoints

The study endpoints are listed in Section 2.

8.2. Planned Analyses

8.2.1. Interim Analysis

8.2.1.1. Planned Internal Unblinded Analysis

The GDRC defined in Section 5.1.3 will perform the data review of study data after 90 subjects complete the Week 10 visit or early discontinuation from the study. Based on the interim analysis, the GDRC may propose changes in the study design, including potential termination of study due to futility. Ad hoc data reviews at additional timepoints may also be conducted by the GDRC if needed.

The study data that will be provided to the GDRC may be unblinded at individual subject level and/or group level, including the following clinical, endoscopic, histologic and biomarker endpoints: Clinical remission per modified MCS, MCS response, endoscopic response, UC-100, Geboes remission, fecal calprotectin, fecal lactoferrin, and CRP.

Additional data may be provided to the GDRC upon request.

If, based on the review of study data, the GDRC concludes that treatment with GS-4875 does not positively impact the disease under study, the GDRC may request an ad-hoc DMC meeting to further evaluate whether continuation of the trial warranted.

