To demonstrate the efficacy of GS-4875, compared with placebo control, in achieving MCS Response at Week 10	MCS Response, defined as a decrease from baseline of ≥ 3 points and at least 30% in MCS, in addition to a ≥ 1 point decrease from baseline in the Rectal Bleeding subscore or a Rectal Bleeding subscore ≤ 1 at Week 10
To demonstrate the efficacy of GS-4875, compared with placebo control, in achieving MCS Remission at Week 10	MCS Remission, defined as a MCS score of ≤ 2 and no individual subscore > 1 at Week 10
To evaluate GS-4875, as compared with placebo control, in achieving histologic remission at Week 10	Histologic remission based upon the Geboes Scale where all of the following must be met at Week 10: Grade 0 of ≤ 0.3 , Grade 1 of ≤ 1.1 , Grade 2a of $\leq 2A.3$, Grade 2b of 2B.0, Grade 3 of 3.0, Grade 4 of 4.0, and Grade 5 of 5.0 (Appendix 5)

Other Secondary Objectives	Other Secondary Endpoints
To evaluate the safety and tolerability of GS-4875	Incidence and characterization of adverse events (AEs) and laboratory abnormalities
	Physical examination (PE) findings, electrocardiogram (ECG), and vital signs

Study Design:

This is a Phase 2, blinded, randomized, placebo-controlled study evaluating the efficacy and safety of GS-4875 for the treatment of subjects with moderately to severely active ulcerative colitis (UC).

This study includes:

- Screening period (Days -30 to -1)
- Baseline/Randomization (Day 1)

Approximately 180 subjects who meet protocol eligibility criteria will be randomized in a 1:1:1 ratio to 1 of 3 treatment groups as follows:

Treatment group 1 (n = 60): GS-4875 300 mg once daily

Treatment group 2 (n = 60): GS-4875 100 mg once daily

Treatment group 3 (n = 60): Placebo once daily

Treatment assignments will be stratified according to the sum (≤ 6 or > 6) of 3 MCS subscores for Stool Frequency, Rectal Bleeding, and Endoscopic Findings at screening.

- Blinded Treatment phase (Day 1 up to Week 50)
 - At Week 10 visit, all subjects will have an efficacy assessment.
- Open-Label (OL) Treatment phase (OL Day 1 up to OL Week 50)
 - At OL Week 10 visit, all subjects will have an efficacy assessment.
- Gilead Data Review Committee (GDRC)
 - After approximately 90 subjects complete the Week 10 visit or discontinue from the study prior to Week 10, the GDRC will review endpoint data for potential study termination due to lack of efficacy.
- Unblinding

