5.1.3. Planned Interim Unblinding

To assess the efficacy of GS-4875 for potential study termination due to lack of efficacy, a Gilead internal unblinded team, the GS-US-365-4237 GDRC, independent of the blinded study team, will be assembled to review the unblinded study results. The GDRC will consist of at least 1 representative from Gilead Clinical Research, Biostatistics, PVE, and Regulatory Affairs, and may include other personnel as necessary including external consultants with expertise in IBD. The GDRC will keep the unblinded information confidential. Site personnel, subjects, Gilead Medical Monitor, Gilead/CRO staff directly interacting with the study center or members of the GS-US-365-4237 Study Management Team will not be unblinded to the subject treatment assignment and will not have access to unblinded study data. The GDRC will be granted access to unblinded clinical data at the individual subject and/or group summary level, including treatment assignments, to review the interim analysis described in Section 8.2.

The membership, conduct, and meeting schedule of the GDRC will be specified in the Gilead Data Review Committee Charter.

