8.7. Adjustments for Multiplicity

There are no interim analyses for efficacy and no plans to stop this study early for favorable efficacy. The following primary and key secondary endpoints will be tested sequentially at a one-sided Type 1 error rate of 2.5% in the following order:

GS-4875 300 mg vs placebo

1. The proportion of subjects with clinical remission per modified MCS at Week 10
2. The proportion of subjects with endoscopic response at Week 10
3. The proportion of subjects with MCS response at Week 10
4. The proportion of subjects with MCS remission at Week 10
5. The proportion of subjects with histologic remission at Week 10

GS-4875 100 mg vs placebo

6. The proportion of subjects with clinical remission per modified MCS at Week 10
7. The proportion of subjects with endoscopic response at Week 10
8. The proportion of subjects with MCS response at Week 10
9. The proportion of subjects with MCS remission at Week 10
10. The proportion of subjects with histologic remission at Week 10

Testing will stop with the first of these endpoints failing to reach statistical significance and all subsequent endpoints would not be considered for statistical significance and only nominal p-values will be reported. In this way, the overall one-sided Type I error rate in testing these endpoints is controlled at a 2.5% level.

CCI [REDACTED]

CCI [REDACTED]

CCI [REDACTED]

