2. TYPE OF PLANNED ANALYSIS

2.1. Interim Analyses

2.1.1. Planned Internal Unblinded Analysis

A Gilead internal unblinded team, the GS-US-365-4237 Gilead Data Review Committee (GDRC), independent of the blinded study team, was to perform the data review of study data after 90 subjects either complete the Week 10 visit or early discontinue from the study. Based on the interim analysis, the GDRC may propose changes in the study design, including potential termination of study due to lack of efficacy.

Ad hoc interim analyses at additional timepoints may also be requested, and data reviews be conducted by the GDRC, if needed.

The membership, conduct, and meeting schedule of the GDRC was to be specified in the GDRC Charter.

Due to small number of subjects enrolled in the study, the planned internal unblinded analysis to be reviewed by GDRC will not be performed.

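### Does letting the unblinded GDRC propose design changes at the halfway review undo the protocol's one-sided 2.5% Type I error control?

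*Protocol*

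**What the plan says.** The GDRC is a sponsor-internal unblinded group, separate from the study team. It reviews data after 90 of about 180 subjects complete Week 10 or discontinue.

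- **Narrower statement.** The synopsis and 3.1 say that "the GDRC will review endpoint data for potential study termination due to lack of efficacy". Protocol 5.1.3 opens with the same purpose: "To assess the efficacy of GS-4875 for potential study termination due to lack of efficacy, a Gilead internal unblinded team". Protocol 1.4 likewise mentions only early termination.
- **Wider statement.** Protocol 8.2.1.1 says: "Based on the interim analysis, the GDRC may propose changes in the study design, including potential termination of study due to futility". It also allows ad hoc reviews. The data listed for the review include the primary endpoint and measures of three of the four key secondary endpoints.
- **Error control.** Protocol 8.7 states: "There are no interim analyses for efficacy and no plans to stop this study early for favorable efficacy". Ten hypotheses, 300 mg before 100 mg, "will be tested sequentially at a one-sided Type 1 error rate of 2.5% in the following order", and the section concludes that "the overall one-sided Type I error rate in testing these endpoints is controlled at a 2.5% level". The final test is a conventional CMH test (8.5.1).
- **SAP.** Section 2.1.1 repeats the wider statement ("Based on the interim analysis, the GDRC may propose changes in the study design, including potential termination of study due to lack of efficacy") and then cancels it: "the planned internal unblinded analysis to be reviewed by GDRC will not be performed".

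**The concern.** On a first reading the protocol gives one committee two remits. If it may only recommend stopping for lack of efficacy, the interim look removes chances to reject and cannot raise the Type I error, so no adjustment is needed. If it may reshape the trial after seeing unblinded remission and response data by group, an unadjusted CMH test is not in general assured of its level. Protocol 8.7 names no combination test, conditional-error rule or list of permitted changes. It denies an efficacy interim without mentioning design changes. At stake would be whether a significant result carries the stated one-sided 2.5% error, in a study meant to inform pivotal Phase 3 trials (3.2.1).

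**Working it through.** **Inputs.** 60 subjects per arm, 1:1:1, remission rates 22.5% and 5%, one-sided 0.025 (8.10); review at 90 of about 180 subjects (8.2.1.1), an information fraction of 90/180 = 0.50, or about 30 per arm; 300 mg tested first (8.7).

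**The plan's own figure.** Exact enumeration of Fisher's test, 60 against 60, 22.5% against 5%, one-sided p ≤ 0.025, gives 75.1% power. The stated figure is approximately 75%, so it reproduces.

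**Termination only.** Let z1 and z2 be independent N(0,1) under the null, one for each half of the data. The final statistic is Z = (z1 + z2)/√2, with rejection if Z > 1.96. The documents give no stopping threshold, so take z1 < 0 as an assumption:

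P(z1 ≥ 0 and Z > 1.96) = ∫ from 0 to ∞ of φ(z)·[1 − Φ(1.96·√2 − z)] dz = 0.0247.

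This is below 0.025, as it must be under any stopping rule that only ends the trial without a rejection.

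**Sample-size growth (assumed; in neither document).** Let r be the second-stage size divided by the first-stage size; the plan has r = 1. Given z1, the unadjusted final test rejects with probability

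1 − Φ((1.96·√(1 + r) − z1)/√r).

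Choosing the most favourable r at every z1 and integrating over N(0,1) gives:

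| Allowed r | Largest total | Type I error |
|---|---|---|
| 1 (as planned) | 180 | 0.0250 |
| 1 to 2 | 180 × 1.5 = 270 | 0.0290 |
| 1 to 3 | 180 × 2 = 360 | 0.0311 |

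The same worst-case rule with exact binomial data (30 per arm at the interim, unstratified CMH z, one comparison) is milder:

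| Common rate | Fixed design | Total up to 1.5 times | Total up to 2 times |
|---|---|---|---|
| 5% | 0.023 | 0.027 | 0.030 |
| 2.5% | 0.014 | 0.023 | 0.026 |

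The 5% is the planning placebo rate; 2.5% is also cited in 8.10.

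**Choosing the leading dose at the interim (assumed; contrary to the fixed order in 8.7).** With a shared placebo arm and no true effect, testing the better-looking interim dose first gives 0.0405 by normal simulation. With binomial data it is 0.035 at a common 5% rate (0.023 in the fixed order) and 0.039 at 10% (0.025 in the fixed order).

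**Changes that keep the level.** An inverse-normal combination test holds 0.025 when the sample size is changed. Dropping 100 mg while 300 mg stays first leaves the leading test intact. So the wider wording does not imply inflation; the outcome depends on what is changed and how it is tested.

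**What the text permits.** The committee may propose. Only the sponsor can modify the protocol, with ethics approval (9.2.1), and a substantial amendment also needs regulatory approval (1.5). The one decision path that 8.2.1.1 spells out runs from no positive effect on the disease to an ad hoc DMC meeting. Neither document describes a sample-size, dose-order or endpoint adaptation.

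**The case for a change.** The strongest case for a change is that three sections state one purpose while the statistical section states a broader one, without any listed limits or an error-preserving test. The committee sees the primary endpoint unblinded by group. Amendment approval does not itself require that a change preserve the error rate. A limit in the charter, which was not available for review, would not reconcile the protocol's own sections. The repair would be cheap: either confine the review to non-binding termination, or list the permitted changes with a suitable test.

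The mismatch stands, and so does the point that 8.7 does not say what would happen to the test if a proposal were adopted. What does not stand is the step from there to a loss of error control. The narrower sections state a purpose and none says it is exclusive; 5.1.3 refers the reader on to 8.2 for the analysis itself. The 2.5% in 8.7 describes the design as written, and nothing says that section would stay untouched in an amendment that changed the design. Every figure above 2.5% comes from a rule supplied by the analyst. Whether to bar design changes outright or keep the option, with suitable testing added if it is used, is a fair sponsor choice in a proof-of-concept Phase 2 study.

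**Conclusion.** No change to the plan is called for. This is a minor inconsistency in how the committee's remit is described. Followed exactly, the protocol keeps one-sided 2.5%: the fixed sequence is tested once on the final data, and stopping for lack of efficacy can only lower the error (2.47% under the assumed z < 0 rule). The illustrative 2.7% to 3.1% for worst-case sample-size growth at the planning rate or on the normal scale, and 3.5% to 4.1% for choosing the leading dose, rest on assumed adaptations combined with a final test left unadjusted; the documents contain neither an adaptation nor a commitment to leave the test unadjusted after one. The practical effect is nil. The study stopped after 19 subjects (SAP 1.2), the GDRC review is cancelled (SAP 2.1.1), no tests are performed (SAP 3.5), and the primary endpoint is only listed by subject (SAP 6.2.2).

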8.2.2. Week 10 Analysis

A Week 10 analysis will be conducted when all randomized subjects (approximately 180) have completed 10 weeks of blinded study drug or discontinued from the study, and associated safety and efficacy assessments have been completed. The study will be unblinded and Week 10 safety and efficacy analyses (including primary analysis [See Section 8.5.1]) will be performed. The purpose of these analyses is to inform study discontinuation or further development of GS-4875 for the treatment of UC. If the sponsor concludes that treatment with GS-4875 has an unfavorable benefit-risk profile, the sponsor will request an ad-hoc DMC meeting. The DMC will be requested to evaluate the available study data and to make recommendation on whether the study should be stopped, continued, or continued with modifications.

8.3. Analysis Conventions

8.3.1. Analysis Sets

8.3.1.1. Efficacy

The primary analysis set for efficacy analysis is the Full Analysis Set (FAS), defined as all randomized subjects who received at least 1 dose of study drug.

Subjects will be analyzed according to the treatment group they were randomized to for the analysis period.

8.3.1.2. Safety

The primary analysis set for safety analyses is the Safety Analysis Set, defined as all subjects who receive at least one dose of study drug.

Subjects will be analyzed according to the study drug they actually received for the analysis period.

All data collected during treatment up to the date of last dose of IMP plus 30 days will be included in the safety summaries.

CCI

CCI

8.3.1.4. Biomarkers

The Biomarker Analysis Set includes all subjects who receive at least one dose of study drug and have the necessary baseline and on-study measurements to provide interpretable results for the specific parameters of interest.

8.4. Data Handling Conventions

Procedures for handling missing data for MCS (and components) will be described in the statistical analysis plan (SAP).

8.5. Efficacy Analysis

8.5.1. Primary Analysis

The primary analysis will compare each GS-4875 dose group to placebo on the proportion of subjects achieving Clinical Remission per Modified MCS at Week 10. The Cochran-Mantel-Haenszel (CMH) approach adjusting for stratification factors will be used for hypothesis testing of the primary endpoint. For evaluation of clinical remission per modified MCS at Week 10, MCS score at screening will be used as baseline value.

Subjects who do not have sufficient measurements to determine efficacy endpoints will be considered failures (ie, non-responder imputation [NRI]).

8.5.2. Secondary Analyses

The same statistical methods used for analyzing the primary efficacy endpoint will be utilized for analyzing the binary secondary endpoints. Subjects who do not have sufficient measurements to determine the efficacy endpoints will be considered failures (ie, NRI).

CCI

[REDACTED]

[REDACTED]

8.6. Safety Analysis

All safety data collected on or after the date that IMP was first dispensed up to the date of last dose of IMP plus 30 days will be summarized by treatment group (according to the IMP received). Data for the pretreatment will be included in data listings.

8.6.1. Extent of Exposure

A subject's extent of exposure to IMP data will be generated from the IMP administration data. Exposure data will be summarized by treatment group.

8.6.2. Adverse Events

Clinical and laboratory AEs will be coded using the Medical Dictionary for Regulatory Activities (MedDRA). System organ class (SOC), High-Level Group Term (HLGT), High-Level Term (HLT), Preferred Term (PT), and Lower-Level Term (LLT) will be attached to the clinical database.

Treatment-emergent adverse event (TEAE) will be defined as 1 or both of the following:

- Any AE with an onset date on or after the study drug start date and no later than 30 days after permanent discontinuation of study drug.
- Any AE leading to premature discontinuation of study drug

Summaries (number and percentage of subjects) of TEAEs (by SOC, and PT) will be provided by treatment group. TEAEs will also be summarized by relationship to study drug and severity. In addition, TEAEs leading to premature discontinuation of study drug will be summarized and listed.

8.6.3. Laboratory Evaluations

Selected laboratory data (using conventional units) will be summarized using only observed data. Absolute value and change from baseline at all scheduled time points will be summarized.

Graded laboratory abnormalities will be defined using the CTCAE in [Appendix 6](#).

Incidence of treatment-emergent laboratory abnormalities, defined as values that increase at least 1 toxicity grade from baseline at any time post baseline, will be summarized by treatment group. If baseline data are missing, then any grade abnormality (ie, at least a Grade 1) will be considered treatment emergent.

8.6.4. Other Safety Evaluations

Individual data for PE findings, prior and concomitant medications and medical history will be provided. Twelve-lead ECGs and vital signs measurements will be listed by subject and summarized by incidence of events/abnormalities or descriptive statistics as appropriate.

8.7. Adjustments for Multiplicity

There are no interim analyses for efficacy and no plans to stop this study early for favorable efficacy. The following primary and key secondary endpoints will be tested sequentially at a one-sided Type 1 error rate of 2.5% in the following order:

GS-4875 300 mg vs placebo

1. The proportion of subjects with clinical remission per modified MCS at Week 10
2. The proportion of subjects with endoscopic response at Week 10
3. The proportion of subjects with MCS response at Week 10
4. The proportion of subjects with MCS remission at Week 10
5. The proportion of subjects with histologic remission at Week 10

GS-4875 100 mg vs placebo

6. The proportion of subjects with clinical remission per modified MCS at Week 10
7. The proportion of subjects with endoscopic response at Week 10
8. The proportion of subjects with MCS response at Week 10
9. The proportion of subjects with MCS remission at Week 10
10. The proportion of subjects with histologic remission at Week 10

Testing will stop with the first of these endpoints failing to reach statistical significance and all subsequent endpoints would not be considered for statistical significance and only nominal p-values will be reported. In this way, the overall one-sided Type I error rate in testing these endpoints is controlled at a 2.5% level.

CCI [REDACTED]

CCI [REDACTED]

CCI [REDACTED]

8.9. Biomarker Analysis

Descriptive statistics of baseline and change in biomarkers will be provided at each sampling time by treatment. To evaluate treatment effect, a mixed-effect analysis of variance model will be used to calculate a point estimate and 2-sided 95% CI for the mean percent change from baseline in biomarker level for each treatment group at individual time points. The estimate and 95% CI of difference in mean percent change from baseline between each GS-4875 dose group and placebo will be provided as well.

CCI [REDACTED]

8.10. Sample Size

A sample size of 60 subjects in the placebo group and 60 subjects in each GS-4875 dose group (n = 120 total for GS-4875) will provide approximately 75% power for each GS 4875 dose group comparison to placebo at a 1-sided 0.025 significance level to detect a treatment difference in clinical remission per modified MCS response rate of 17.5% (22.5% on GS-4875 and 5% on placebo) based on Fisher's exact test.

Study GS-US-365-4237 compares GS-4875 to placebo in subjects who previously demonstrated an inadequate response or loss of response to a TNF α inhibitor (TNF α failures). Results from previously conducted studies indicate that placebo response rates for TNF α failures are low, 2.5% to 6.9%, compared to the rates for subjects naive to TNF α inhibitors, 8.7% to 11% {Sandborn 2020a, Sandborn 2012}. Further, across available clinical study results, the definition for clinical remission can vary between studies. For Study GS-US-365-4237, the definition for clinical remission is nearly identical to that used by 2 recently published studies in which the placebo response rates in TNF α failures subgroups were 2.5% and 0% {Sandborn 2020a, Sandborn 2020b}. Accordingly, a conservative placebo response rate of 5% has been utilized in the sample size calculation.

To justify further development, GS-4875 should be as good or better than other drug candidates in development or on the market. A minimum treatment difference of 17.5% was selected for Study GS-US-365-4237 based on data from a similar Phase 2 study in UC which demonstrated a 19.6% treatment difference between study drug and placebo as assessed by Clinical Remission per the Modified Mayo Clinical Score {Sandborn 2020b}. The patient population in this study consisted mainly of biologically experienced subjects (78%) and thus should be similar to the patient population enrolled in Study GS-US-365-4237. In summary, a treatment difference of 17.5% and a placebo response rate of 5% is assumed in the sample size calculation for GS-US-365-4237.

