A Week 10 analysis will be conducted when all randomized subjects (approximately 180) have completed 10 weeks of blinded study drug, or discontinued from the study, and associated safety and efficacy assessments have been completed. The study will be unblinded and safety analysis and Week 10 efficacy analysis (including primary analysis) will be performed. The purpose of these analyses is to inform study discontinuation or further development of GS-4875 for the treatment of UC. If the sponsor concludes that treatment with GS-4875 has an unfavorable benefit-risk profile, the sponsor will request an ad hoc DMC meeting. The DMC will be requested to evaluate the available study data and to make recommendation on whether the study should be stopped, continued, or continued with modifications.

Adjustments of Multiplicity

The following primary and key secondary endpoints will be tested sequentially at a one-sided Type 1 error rate of 2.5% in the following order:

GS-4875 300 mg vs placebo

1. The proportion of subjects with clinical remission per modified MCS at Week 10
2. The proportion of subjects with endoscopic response at Week 10
3. The proportion of subjects with MCS Response at Week 10
4. The proportion of subjects with MCS Remission at Week 10
5. The proportion of subjects with histologic remission at Week 10

GS-4875 100 mg vs placebo

6. The proportion of subjects with clinical remission per modified MCS at Week 10
7. The proportion of subjects with endoscopic response at Week 10
8. The proportion of subjects with MCS response at Week 10
9. The proportion of subjects with MCS remission at Week 10
10. The proportion of subjects with histologic remission at Week 10

Testing will stop with the first of these endpoints failing to reach statistical significance and all subsequent endpoints would not be considered for statistical significance and only nominal p-values will be reported.

Sample Size

A sample size of 60 subjects in the placebo group and 60 subjects in each GS-4875 dose group (n = 120 total for GS-4875) will provide approximately 75% power for each GS-4875 dose group comparison to placebo at a 1-sided 0.025 significance level to detect a treatment difference in Clinical Remission per modified MCS response rate of 17.5% (22.5% on GS-4875 and 5% on placebo) based on Fisher's exact test.

This study will be conducted in accordance with the guidelines of Good Clinical Practice (GCP) including archiving of essential documents.

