GS-US-365-4237 is a proof-of-concept study of GS-4875, a first-in-class TPL2 inhibitor, in subjects with UC. In consideration of this early stage of development for GS-4875 with a novel and unproven mechanism of action, periodic assessments of GS-4875 safety and efficacy will be performed in this study by the independent DMC and GDRC, respectively. Neither of these committees will include personnel involved in the conduct of the study. Early periodic efficacy and safety assessments in this Phase 2 proof-of-concept study with GS-4875 will appropriately balance the safety of subjects that participate in this clinical trial with the ability to inform pivotal Phase 3 clinical trials based on the results from an adequately powered and blinded study.

When all randomized subjects (approximately 180) have either completed the Blinded Treatment phase Week 10 visit and all associated efficacy and safety assessments, or discontinued the study before Week 10, a Week 10 safety and efficacy analysis will be performed to inform study discontinuation or further development of GS-4875 for the treatment of UC. For further details, see Section 8.2.2 Week 10 Analysis.

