5.3.1. Rationale for Dose Selection

Given the novelty of targeting the TPL2 pathway, GS-4875 dose selection was guided by the goal to demonstrate a dose/exposure efficacy relationship. The 300 mg dose was selected such that trough drug levels, based on Phase 1 data, would be EC₆₀ for the in vitro LPS-stimulated phosphorylated ERK (pERK) assay in human whole blood. The 100 mg dose was selected such

that simulations of trough drug levels, which were based on the Phase 1 data, would be EC₅₀ at trough. The selection of these doses of GS-4875 (100 and 300 mg) is supported by the safety and PK data in the first-in-human Study GS-US-365-4233.

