1. INTRODUCTION

This statistical analysis plan (SAP) describes the statistical analysis methods and data presentations to be used in tables, figures, and listings (TFLs) in a synoptic clinical study report (CSR) for Study GS-US-365-4237. This SAP is based on the study protocol Amendment 2 dated 19 June 2020 and the electronic case report form (eCRF). The SAP will be finalized prior to data finalization for the primary analysis. Subject enrollment in Study GS-US-365-4237 was terminated early by Gilead. Data Monitoring Committee (DMC) meetings and Gilead Data Review Committee (GDRC) meetings will not be held for this study due to small number of subjects enrolled in this study. As well, some of the statistical analyses and all statistical testings planned in the study protocol will not be performed. Any changes made after the finalization of the SAP will be documented in the synoptic CSR.

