1.3. Sample Size and Power

A total of 180 subjects, i.e. 60 subjects in the placebo group and 60 subjects in each GS-4875 dose group (n = 120 total for GS-4875), will provide approximately 75% power when comparing each GS-4875 dose group to placebo at a 1-sided 0.025 significance level to detect a treatment difference in clinical remission rate per modified MCS of 17.5% (22.5% on GS-4875 and 5% on placebo) based on Fisher's exact test.

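### The 75% power given for each dose is stand-alone pairwise power; under the fixed testing sequence the 100 mg primary test has at most about 61% on the same inputs

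*Protocol*

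**What the plan says.** Protocol Section 8.10 states that 60 subjects per arm "will provide approximately 75% power for each GS 4875 dose group comparison to placebo at a 1-sided 0.025 significance level". The assumed remission rates are 22.5% on GS-4875 and 5% on placebo, a difference of 17.5 points, tested with Fisher's exact test. One active rate serves both doses. The Sample Size paragraph of the synopsis makes the same statement ("will provide approximately 75% power for each GS-4875 dose group comparison to placebo at a 1-sided 0.025 significance level"), and so does SAP Section 1.3 ("will provide approximately 75% power when comparing each GS-4875 dose group to placebo at a 1-sided 0.025 significance level").

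Protocol Section 8.7, like the synopsis, sets a single fixed sequence of ten tests, each at one-sided 2.5%. Steps 1 to 5 compare 300 mg with placebo on the primary endpoint and four key secondary endpoints. Steps 6 to 10 repeat these for 100 mg. The stopping rule is: "Testing will stop with the first of these endpoints failing to reach statistical significance". Whatever comes after a failure receives only a nominal p-value.

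None of the three power statements refers to this sequence.

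The planned primary test is also not the one used for sizing: under Section 8.5.1 a CMH "approach adjusting for stratification factors will be used for hypothesis testing of the primary endpoint".

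**The concern.** The power statements present the two doses as equally covered at the one-sided 0.025 level. Under Section 8.7 they are not. Nothing precedes the 300 mg primary test, so its power in the sequence equals its pairwise power. The 100 mg primary test can support a formal claim only after five earlier successes, so on equal assumed effects its power must be lower.

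What is at stake is how the design is read. Section 3.2.1 speaks of informing Phase 3 "based on the results from an adequately powered and blinded study". A reader who takes 75% as the chance of a formal 100 mg finding would give too much weight to a non-significant or merely nominal 100 mg result, and anyone reusing the design would inherit the overstatement. Control of the Type I error is not in question.

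**Working it through.** **Inputs.** From Section 8.10: n = 60 per arm, placebo rate 0.05, active rate 0.225 for either dose, one-sided α = 0.025, Fisher's exact test. From Section 8.7: the order of tests and the stopping rule. The design is 1:1:1, so both doses share one placebo arm.

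**Step 1: reproduce the stated 75%.** For x remitters on active drug and y on placebo, Fisher's one-sided p-value is P(X ≥ x), where X is hypergeometric (x + y remitters among 120 subjects, 60 of them on active drug). Let A(y) be the probability, with x distributed Binomial(60, 0.225), that this p-value is at most 0.025. Then

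pairwise power = Σ_y b(y; 60, 0.05) · A(y) = **75.1%**.

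The stated figure is reproduced.

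**Step 2: require steps 1 and 6 both to succeed.** Given the shared placebo count y, the two comparisons are independent. With equal active rates,

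joint power = Σ_y b(y; 60, 0.05) · A(y)².

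| y | b(y) | Smallest significant x | A(y) | b·A | b·A² |
|---|---|---|---|---|---|
| 0 | 0.0461 | 6 | 0.9964 | 0.0459 | 0.0458 |
| 1 | 0.1455 | 8 | 0.9743 | 0.1418 | 0.1381 |
| 2 | 0.2259 | 10 | 0.8954 | 0.2023 | 0.1811 |
| 3 | 0.2298 | 11 | 0.8222 | 0.1889 | 0.1554 |
| 4 | 0.1724 | 13 | 0.6113 | 0.1054 | 0.0644 |
| 5 | 0.1016 | 14 | 0.4886 | 0.0496 | 0.0243 |
| 6 | 0.0490 | 16 | 0.2625 | 0.0129 | 0.0034 |
| 7 | 0.0199 | 17 | 0.1756 | 0.0035 | 0.0006 |
| All y | | | | **0.7511** | **0.6131** |

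The ceiling for the 100 mg primary test is **61.3%**, which is 75.1 − 61.3 = 13.8 points below the pairwise value. A simulation of 1,000,000 trials also gave 61.3%. Treating the two comparisons as independent, which ignores the shared placebo arm, would give 0.7511² = 56.4%.

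**Step 3: steps 2 to 5.** The documents give no rates for these endpoints, and they are correlated with the primary (every clinical remitter is by definition an endoscopic responder), so their cost cannot be computed. As an illustration only, suppose each succeeds with probability 0.95, given the earlier steps and step 6. The 100 mg power is then 0.613 × 0.95⁴ ≈ 50%; with 0.90 it is 0.613 × 0.90⁴ ≈ 40%.

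**Step 4: sensitivity to the 300 mg rate.** No separate 300 mg rate is given, so the rates here are assumptions (Fisher; 100 mg held at 22.5%, placebo at 5%):

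| Assumed 300 mg rate | Ceiling for 100 mg |
|---|---|
| 20% | 52.6% |
| 22.5% | 61.3% |
| 25% | 67.3% |
| 30% | 73.2% |
| 40% | 75.1% |

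The ceiling approaches the pairwise value but never exceeds it.

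**Step 5: sensitivity to the placebo rate.** Section 8.10 quotes 2.5% to 6.9% for earlier TNFα failures. With the difference held at 17.5 points in both dose arms, Fisher gives 84.0% pairwise and a 73.2% ceiling at 2.5%, and 69.4% pairwise and a 54.4% ceiling at 6.9%.

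**Step 6: the planned CMH test.** The protocol does not say whether a continuity correction applies. In single-stratum form at the base rates:

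- Uncorrected: 82.8% pairwise, 72.4% ceiling (77.1% if 300 mg is 25%, about 81% if it is 30%).
- Continuity-corrected: 75.1% pairwise, 61.3% ceiling, the same as Fisher.

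A two-stratum simulation, assuming equal rates in both strata and a stratum share of 20% to 70%, moved these figures by less than half a point.

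**The case against.** The strongest reply is that the statement is not false on its own terms. It speaks of each comparison with placebo by Fisher's exact test, and that is pairwise power, correctly calculated. The sequence is openly stated, and in the synopsis it stands directly above the sample-size paragraph. This much stands: no calculation was done wrongly, and what is missing is the link between the two statements.

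A second reply is that equal effects may be the wrong assumption. Section 5.3.1 says that "GS-4875 dose selection was guided by the goal to demonstrate a dose/exposure efficacy relationship", which points to a stronger effect at 300 mg and a cheaper gate. With uncorrected CMH and 300 mg at 25%, the ceiling is 77.1%, above the stated 75%. That also stands as a limit on the 61% figure. But the protocol's own power statement uses one rate for both doses, and 77.1% should be set against the 82.8% pairwise power of the same test. Like for like, the gate never helps 100 mg.

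Third, 61% is itself not the power, because steps 2 to 5 are left out. Correct, and for that reason it should be written only as an upper bound.

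Fourth, the phrase about adequate power in Section 3.2.1 belongs to a general remark on a proof-of-concept trial and does not claim equal power for both doses. That is fair; it is context, not a contradiction.

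Finally, nothing now depends on the number. SAP Section 1.2 records 19 subjects enrolled, Section 3.5 drops all testing and Section 6.2.2 provides only a listing. This stands in full and limits the point to the accuracy of a stated design figure.

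**Conclusion.** The concern holds. The 75% is correct as the power of one stand-alone Fisher test and, within the sequence, for 300 mg. It is not the power of the 100 mg primary test under Section 8.7, which on the protocol's own inputs is at most about 61%. The 61% rests on 60 per arm, 22.5% on both doses, 5% on placebo and Fisher's test at one-sided 0.025, and it ignores steps 2 to 5. Under uncorrected CMH the ceiling is about 72% against about 83% pairwise, a gap of about 10 points. The gap narrows if 300 mg is assumed more effective. No reported result or analysis is affected, although the SAP, finalised after enrolment was terminated, still carries the figure.

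**What to change.** Amend the synopsis, Protocol Section 8.10 and SAP Section 1.3 along these lines:

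> The figure of approximately 75% is the power of a single Fisher's exact test and, under the Section 8.7 sequence, applies to the 300 mg primary test. The 100 mg primary test is reached only if tests 1 to 5 succeed. If both doses have the same effect, its power is at most about 61% (Fisher), before tests 2 to 5 are taken into account. This ceiling rises if 300 mg is assumed to be more effective than 100 mg.

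If a figure for the planned CMH test is quoted, name the variant: a ceiling of about 72% without continuity correction, about 61% with it.

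If the documents are not to be reopened, a note in the synoptic clinical study report is enough. SAP Section 1 already provides for this: "Any changes made after the finalization of the SAP will be documented in the synoptic CSR".

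The cost is wording in three places or one note. The 100 mg figure becomes less favourable. No patients, data or analyses change.
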